7.1 ITT population

Treatment of missing values:

- Subjects missing data "not in random" will be imputed as "failure" on dichotomous endpoints.
- "Failures" (not MAR) include:
 - Subject leaves the study due to related AE
 - Device explant
 - o Lack of effect that results in significant increase of UUI medication
 - Need for other 3rd line therapies for the management of UUI

Document ID	Revision / Date	Page
G02-CLP-0009	Rev. 06 / 18 May 2022	11 of 26

- Baseline values will not be imputed
- Missing values in ITT not due to "failure" will be imputed using multiple imputation (MI).

Multiple imputation will be applied to the primary and three secondary endpoints. The 'additional endpoint' analyses will not use multiple imputation. The imputation procedure will be performed on the continuous outcomes (e.g. number of incontinence episodes). Based on the imputed continuous outcome, the response will be defined accordingly for each endpoint.

The hypotheses will be tested by performing the logistic regression on each imputed dataset. Then SAS PROC MIANALYZE procedure will be used to calculate the combined confidence interval and the corresponding p-value. The evaluation on each endpoint will be successful if the lower limit of the confidence interval is above 50%. In addition, the primary analysis will present the observed frequency of responders and descriptive statistics of response rates over all imputed datasets.

Fifty (50) imputed datasets will be created (the seed is set to 123456).

The imputation will be done using covariates: Age, BMI, average number of urgency leaks, average number of urgent voids, HRQL score and OAB duration at baseline. This list might be reduced if the model fails to converge.

Because MI assumes missing at random (MAR), sensitivity analyses (i.e. tipping point) described below, will be conducted to test the effects of other patterns of missingness.

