8.3 Secondary Efficacy Endpoints

The following will be assessed as formal secondary efficacy endpoints

 Proportion of subjects with ≥10 points (MID) improvement compared to baseline in HRQL (based on OAB-q) at 6 months post system activation

This endpoint is defined dichotomously as follows:

Success ("1") If the absolute improvement (increase) in HRQL from baseline is ≥10 points (MID)

Failure ("0") Otherwise

Proportion of responders at 12 months post system activation as demonstrated by ≥50% improvement in either average number of urgency related incontinence episodes or average number of large (severe) urgency related incontinence episodes, as measured by 7-day Patient Voiding Diary.

This endpoint is defined dichotomously as follows:

Success ("1") If the percent reduction in either average number of urgency-related leaks per day *or* average number of large urgency-related leaks per day from baseline to 12 months follow-up is ≥50%

Failure ("0") Otherwise

Proportion of responders at 6 months post system activation as demonstrated by ≥50% improvement in the average number of moderate-severe urgency episodes PPIUS degree 3,4 or <8 voids/day

This endpoint is defined dichotomously as follows:

Success ("1") If either the percent reduction in average number of moderate-severe urine

Document ID	Revision / Date	Page
G02-CLP-0009	Rev. 06 / 18 May 2022	14 of 26

output episodes with PPIUS degree 3,4 per day (i.e. average number urine output episodes with urgency level above 2) from baseline to 6 months is \geq 50% **or** the average number of total voids per day is less than 8 at 6 months

Failure ("0")

Otherwise

This endpoint is defined only for patients with baseline number of voids per day of at least 8 and baseline number of urgent episodes (PPIUS 3 or 4) of at least 9 per 7-day diary.

Missing data for the secondary endpoints will be imputed according to Section 7.1, above.

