12.8 Covariate, Subgroup, and 'Poolability' Analyses

Covariate analyses will be done by comparing the primary endpoint by the levels of the covariate at baseline, where continuous variables will be coded into two levels by median split. Analyses will be done by logistic regression. Covariates will include, but are not limited to:

- Age
- BMI
- OAB duration at baseline
- US vs. Outside of US (OUS)
- Race and ethnicity
- Baseline average urgency leaks/day
- Baseline average voids/day
- Smoking history (Past/Current/Never)
- Concomitant OAB medication at time of screening
- Ratio between average stress related leaks and average urgency related leaks at baseline.

For each of the listed above covariates descriptive statistics of the primary endpoint by covariate levels will be

Document ID	Revision / Date	Page
G02-CLP-0009	Rev. 06 / 18 May 2022	23 of 26

presented. Continuous covariates will be divided into quartiles for this presentation. Additionally, formal subgroup analyses will be conducted to assess the effects on the primary endpoint of antidepressant medications and OAB medication, and also to assess the potential impact of COVID-19 on the study outcomes.

The analyses for antidepressant medications and OAB medications will be structurally similar. The first level of the analyses for each medication type will compare treatment effect (success rates) among those taking and not taking the respective medication at baseline. This will be performed as a logistic regression model, with baseline status as an indicator variable. If there is no difference in outcome, the second level of the analysis will be a logistic regression analysis on all subjects, with an indicator variable for changes in medication (lower, same or higher total dosage). If there is a differential effect concerning baseline status, the second level analysis will be comprised of two analyses; one only consisting of the subjects on the respective medication at baseline, with an indicator for any subsequent changes, and this will be repeated for the complementary subgroup of those subjects not on the respective medication at baseline. For each level of analysis, the success rate for each level of the subgroup will be reported for completeness. It should be noted that changes in usage of antidepressants and OAB medications will need to be defined and filtered from the concomitant medications form in exploratory fashion.

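### The SAP 7.1 imputation model should include baseline total voids/day and baseline large urgency leaks/day for the two secondary endpoints that use them

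*SAP*

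**What the plan says.** SAP 7.1: "Multiple imputation will be applied to the primary and three secondary endpoints". The covariates are "Age, BMI, average number of urgency leaks, average number of urgent voids, HRQL score and OAB duration at baseline", and "This list might be reduced if the model fails to converge". No variable is protected from that reduction. Imputation is on the continuous scale, after which "Based on the imputed continuous outcome, the response will be defined accordingly for each endpoint". Baseline values are not imputed. SAP 8.3 refers missing secondary data back to 7.1.

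Two of the three secondary endpoints in SAP 8.3 are either/or composites:

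- **6-month urgency/frequency endpoint.** Success is a reduction of at least 50% in PPIUS 3–4 episodes, or "the average number of total voids per day is less than 8 at 6 months". It is defined only for women with at least 8 voids/day and at least 9 urgent episodes per 7-day diary at baseline.
- **12-month endpoint.** Success is a reduction of at least 50% in urgency leaks, or in "average number of large urgency-related leaks per day from baseline to 12 months follow-up".

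SAP 12.8 lists "Baseline average voids/day" among the covariates for the primary endpoint, so that variable is derived anyway. Protocol 13.3 has a shorter, non-binding imputation list that also lacks both baselines.

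**The concern.** The baseline of a diary variable is normally among the best predictors of its follow-up value. The list carries the matching or nearest baseline for the other imputed quantities (urgency leaks, urgent voids, HRQL) but not for total voids or large leaks. The gap therefore looks like an oversight.

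Two things follow. First, women who agree on the six listed covariates but differ in baseline voids/day get the same imputed distribution of 6-month voids, and so the same imputed chance of falling below 8. Likewise, 12-month large leaks are drawn without regard to baseline large leaks and then compared with that baseline. Second, dropout related to an omitted baseline, given the listed covariates, would be missing at random with that baseline in the model but need not be without it.

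Both endpoints are formally tested (goals of 45% and 50%, SAP 12.6.2), and the urgency/frequency endpoint is the stated reason for enrolling 150 women. The tipping-point analysis in SAP 12.7 addresses only the primary outcome, so it would not expose the problem.

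**Working it through.** **1. Is the baseline of each imputed variable in the model?**

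| Endpoint | Follow-up variable to impute | Own baseline listed in SAP 7.1? |
|---|---|---|
| Primary, 6 months | urgency leaks/day | yes |
| HRQL, 6 months | HRQL score | yes |
| Urgency/frequency, 6 months | PPIUS 3–4 episodes/day | nearest match: urgent voids |
| Urgency/frequency, 6 months | total voids/day | **no** |
| 12 months | urgency leaks/day | yes |
| 12 months | large urgency leaks/day | **no** |

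**2. The plan's own figure.** SAP 9 gives 89 evaluable women for the urgency/frequency endpoint (61% against 45%, one-sided 0.025, power at least 85%). The exact binomial test rejects at 50 or more of 89, with alpha 0.0223 and power 0.851. Then 89/0.85 = 104.7, rounded up to 105, and 105/0.70 = 150. All agree with the SAP, and none depends on the imputation model.

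**3. Size of the bias.** The documents give no distributions, so all means, SDs and correlations here are assumed. The method was multiple imputation by Bayesian normal regression with 15% missing. The baseline-to-follow-up correlation ran from 0.3 to 0.7, and the correlation between the listed and the omitted baseline was 0.3 or 0.6. Missingness was either unrelated to the omitted baseline or had log-odds changing by 1.0 per SD of it. The model held the listed counterpart (urgent voids or urgency leaks), with or without the omitted baseline. Age, BMI, HRQL and OAB duration were not simulated. The large-leak runs used n = 150, 500 trials and 20 imputations, with baseline large leaks floored at one per 7-day diary.

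Bias = mean imputed response rate minus mean full-data rate, in percentage points overall:

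| Endpoint | Who is missing more often | Omitted baseline left out | Omitted baseline added |
|---|---|---|---|
| Urgency/frequency | unrelated | −0.3 to 0.0 | −0.2 to +0.1 |
| Urgency/frequency | women with many voids | +0.4 to +1.1 | −0.1 to +0.1 |
| Urgency/frequency | women with few voids | −1.4 to −0.5 | −0.2 to 0.0 |
| 12 months | unrelated | −0.4 to −0.2 | −0.6 to −0.5 |
| 12 months | women with many large leaks | +0.4 to +1.6 | −0.2 to 0.0 |
| 12 months | women with few large leaks | −1.4 to −1.1 | −1.1 to −0.8 |

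The largest value, +1.6, is 75.5% imputed against 73.9% true. The bias left in the 12-month rows after the baseline is added comes from fitting a normal model to skewed counts.

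**4. A second method for voids.** Predictive mean matching was run with n = 105, 15% missing, correlation 0.5 between the two baselines, a log-odds change of 0.7 per SD, 250 trials and 10 imputations.

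- Missingness rising with baseline voids: true 57.1%. Without baseline voids 58.5% (+1.4); with it 57.5% (+0.4).
- Missingness falling with baseline voids: true 56.5%. Without 55.7% (−0.8); with 56.5% (0.0).

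**5. Scale.** 1.4 points of 105 is 0.014 × 105 = 1.5 women, and 1.6 points of 150 is 0.016 × 150 = 2.4 women. At n = 105 and 57% response, the standard error is √(0.57 × 0.43/105) = 4.8 points. The planned margin is 61 − 45 = 16 points. Overall bias is the imputed fraction times the bias among the imputed. So if, say, a third of the 15% were set to failure, 1.6 would shrink to 1.6 × 2/3 = 1.1 points.

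**The case against.** Several stronger readings are tempting, and the documents do not support them.

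- **That imputed responses ignore each woman's starting value.** They do not. Urgent voids and urgency leaks at baseline are in the model. They serve the other half of each composite and are plausible proxies for what is missing. Large-leak response is still calculated from her own observed baseline; only the imputed follow-up count is not conditioned on it. The under-8 cut is an absolute threshold, so what is lost there is prediction.
- **That the missing-at-random assumption fails.** It fails on this account only if missingness depends on the omitted baseline after the listed covariates are taken into account. Nothing in the documents says that it does.
- **That the result is tilted towards the device.** The sign depends on who drops out.

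It is also fair to say that 15% overstates the imputed fraction if that is the total attrition. SAP 7.1 first sets to failure those missing because of explant, related-AE exit, lack of effect with a significant increase in UUI medication, or need for third-line therapy. The secondary endpoints are tested only after primary success. No run here shows a changed success decision, type I error or power.

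All of this stands and limits the size of the point. One further defence helps less: the per-protocol analysis uses observed values and so gives a comparison without imputation. In the voids simulation, observed-case rates erred in the same direction. With correlations 0.3 (between baselines) and 0.7 (baseline to follow-up), and women with many voids missing more often, the full-data rate was 47.8%, the observed-case rate 49.4% and the imputed rate without baseline voids 48.9%. Agreement between the two analyses would therefore not show that the omission is harmless.

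For large leaks the case for change is weaker. Adding the baseline removes the bias in one setting, helps slightly in another, and makes it slightly worse when missingness is unrelated to that baseline.

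**Conclusion.** The point holds as a modest, inexpensive improvement to the imputation of two secondary endpoints. The omission can be read directly from SAP 7.1 and 8.3. Its effect is conditional: up to about 1.4 points for urgency/frequency and 1.6 points for the 12-month endpoint, in either direction, if missingness depends on the omitted baseline beyond the listed covariates, and almost nothing otherwise. These sizes rest on assumed distributions, correlations and missingness slopes with 15% imputed. Simulating the other listed covariates could reduce them further. The primary endpoint, the HRQL endpoint and the 89/105/150 calculation are unaffected. The convergence clause does reach every endpoint, because as written it would allow even the baselines now listed to be dropped.

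**What to change.** In SAP 7.1, before database lock:

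1. Add baseline average total voids/day to the imputation model for the 6-month urgency/frequency endpoint. Every woman in that analysis has the value, because it decides her inclusion.
2. Add baseline average large urgency leaks/day to the model for the 12-month endpoint. The gain is smaller and partial. The value is already needed as the denominator of the percent reduction.
3. State that, if the list is reduced for convergence, the baseline of the variable being imputed is kept.

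The cost is two existing variables in the imputation code and one sentence in the SAP. No new data are collected and the sample size does not change.

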7.2 Per Protocol Population

Only observed values will be used in PP. Thus, the primary endpoint will be analyzed in PP only on those subjects with an observed primary endpoint. Similarly, a subject will be included in the analysis of a secondary endpoint only if she has an observed value on that endpoint.

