13.2.2 Per Protocol analysis set

The per protocol analysis set (PP) will be a subset of ITT population without major protocol violations, where "major" is defined has having the potential to meaningfully affect outcome. Also excluded will be subjects who received treatment on fewer than 50% of days during which they were eligible for therapy delivery.

Only observed values will be used in the endpoint analyses for the PP. Thus, the primary endpoint will be analyzed only on those subjects with an observed primary endpoint. Similarly, a subject will be included in the analysis of a secondary endpoint only if she has an observed value on that endpoint.

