13.3 Treatment of Missing Data for Efficacy Analyses

Frequency of missing data and the reasons for the missing data will be presented in the final report. For ITT effectiveness endpoints, a multiple imputation procedure will be used to impute missing endpoint data. Any patients missing endpoint data due to "failure" will be considered as a failure for the effectiveness analysis. Further sensitivity analyses will include, but may not be limited to, a tipping-point analysis for handling missing data.

Baseline variables included in the multiple imputation procedure may consist of:

- Age
- Number of UUI episodes per day
- OAB duration
- Number of prior attempted OAB treatments

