6.1.1 Per Protocol Population (PP)

The per protocol analysis set (PP) will be a subset of ITT subjects with observed data on the endpoint analyzed. Excluded will be subjects with major protocol violations, where "major" is defined has having the potential to meaningfully affect outcome. A list of major protocol violations, as assessed by qualified personnel who is masked to patient outcomes will be provided by the Sponsor prior to database lock. Subjects with a major protocol violation will be excluded globally in the PP population.

Also excluded from per visit analyses will be subjects with less than 50% compliance (i.e. those who received treatment on fewer than 50% of days during which they were eligible for therapy delivery) for the period prior to the visit. These will be local exclusions for the timepoint the subject is considered non-compliant.

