7.3 OR1 Population

Missing primary endpoint data will be imputed using MI, as described above. For all other endpoints, only observed data will be used for the OR1 population.

8 Definition of Endpoints

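### The per-protocol analyses and the one-month-responder secondary endpoints leave out women with missing data whom the SAP scores as failures in ITT, so these supportive rates are biased upward

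*SAP*

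**What the plan says.** **ITT.** SAP 7.1 sets the rule: "Subjects missing data 'not in random' will be imputed as 'failure' on dichotomous endpoints". Four categories count as failure. They include "Subject leaves the study due to related AE" and "Need for other 3rd line therapies for the management of UUI"; the other two are device explant, and lack of effect leading to a significant increase in UUI medication. All other missing values are multiply imputed. Protocol 13.3 agrees: "Any patients missing endpoint data due to 'failure' will be considered as a failure for the effectiveness analysis". Both texts are written for ITT. SAP 7.1 carries that heading, and the sentence before the one quoted from Protocol 13.3 refers to ITT effectiveness endpoints.

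**PP.** SAP 6.1.1 makes an observed value a condition of membership: the set "will be a subset of ITT subjects with observed data on the endpoint analyzed". SAP 7.2 repeats this: "the primary endpoint will be analyzed in PP only on those subjects with an observed primary endpoint". So does Protocol 13.2.2: "Only observed values will be used in the endpoint analyses for the PP".

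**OR1.** SAP 7.3 applies multiple imputation to the primary endpoint by reference back to 7.1. It then adds: "For all other endpoints, only observed data will be used for the OR1 population".

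**Use.** SAP 12.6.2 repeats the primary analysis in PP and OR1 and analyses the secondary endpoints in ITT, PP and OR1. Protocol 13.5.1 calls the PP analyses supportive. Protocol 13.2.3 gives OR1 the purpose of qualitative comparison with treatments that use a trial period before permanent implantation.

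**Competing text.** SAP 8.3 sends missing secondary endpoints to section 7.1 without naming a population. SAP 12.6.2, which covers all three sets, says that secondary testing follows the primary as regards multiple imputation.

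**The concern.** A per-protocol set is meant to show the result in women who followed the protocol. As written, PP also loses women who followed it but whose treatment ended for a reason that the SAP regards as informative. Take a compliant woman with no violation, explanted at month 4 and without a 6-month diary. She is a failure in ITT and absent from PP.

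The direction of the bias is fixed. Removing women who would count as non-responders raises any non-zero rate. In a single-arm trial against a fixed goal, no control arm carries the same bias to offset it. What is at stake is the supportive evidence: PP could appear to confirm the 50% goal when the same women, with failures counted, would not meet it. In OR1, leaving out late failures would flatter the comparison with trial-period treatments.

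**Working it through.** **Inputs.** Goal 50%, one-sided 0.025, assumed response 65%, attrition 15% (Protocol 13.4); 114 evaluable (SAP 9); 150 enrolled; pilot explants 1 of 36 (Protocol 7.2). The share of attrition that would be failure is not given, so it is varied.

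**The plan's own figure.** The documents state no PP or OR1 rate, so the check starts from the sample size. Exact binomial, n = 114: success needs at least 68 responders, P(X ≥ 68 | 0.50) = 0.0244 and P(X ≥ 68 | 0.65) = 0.9015. The 114 reproduces at the protocol's 90% power.

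**Effect on the rate.** With x responders among N women, of whom f are failures without a diary, the failures-included rate is x/N and the observed-case rate is x/(N − f). The ratio of the second to the first is 1/(1 − f/N).

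**Effect on the threshold.** For n = N − f, find the smallest x with P(X ≥ x | n, 0.50) ≤ 0.025. This is the same as a Clopper-Pearson lower 97.5% bound above 50% (Protocol 13.5.4).

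Assume N = 150, 90 responders (60%), all missing women being listed failures and no other PP exclusions. For the first assumed f, 150 × 1/36 = 4.2, taken as 4. For the last, 150 × 0.15 = 22.5, taken as 22.

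| f dropped | n | 90/n | Responders needed | As % of 150 | Lower bound of that count over 150 |
|---|---|---|---|---|---|
| 0 | 150 | 60.0% | 88 | 58.7% | 50.35% |
| 4 | 146 | 61.6% | 86 | 57.3% | 49.01% |
| 10 | 140 | 64.3% | 83 | 55.3% | 47.01% |
| 15 | 135 | 66.7% | 80 | 53.3% | 45.02% |
| 22 | 128 | 70.3% | 76 | 50.7% | 42.39% |

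At 90 responders the goal is met either way (lower bound of 90/150 = 51.7%), so only the reported rate changes. The conclusion changes in a band below 88. With 4 dropped, 86 or 87 responders pass in PP but not over 150. With 10 dropped, the band is 83 to 87.

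**At the design rate.** Observed 74/114 = 64.9% (lower bound 55.4%). Adding failures back as non-responders:
- 3 added (114/36 ≈ 3): 74/117 = 63.2% (53.8%)
- 10 added: 74/124 = 59.7% (50.5%)
- 12 added: 74/126 = 58.7% (49.6%)
- 20 added (all planned attrition, 134 − 114): 74/134 = 55.2% (46.4%)

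At the assumed 65% it therefore takes about 12 failures beside 114 observed women before PP and the failures-included result disagree.

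**OR1 secondary endpoints.** If p is the observed-case rate and φ the failure share, the inflation is p × φ. For assumed p of 65% to 85%, that is 1.8 to 2.4 points at φ = 1/36 and 6.5 to 8.5 points at φ = 10%. The pilot figure is only a loose guide here. That explant came two weeks after implantation, before activation, and such a woman would have no one-month diary and would never enter OR1.

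**The case against.** The case for leaving the text alone is substantial, and most of it stands as a limit on the point.

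- **No trial decision depends on it.** Success is judged in ITT with the failure rule. A favourable PP result cannot rescue a failed ITT result. This stands.
- **Observed-case PP is a common convention**, stated consistently in SAP 6.1.1, SAP 7.2 and Protocol 13.2.2. A reader might infer from Protocol 13.3 that PP breaks a general rule for the effectiveness analysis. The documents do not support that, because the rule is written for ITT and nothing is contradicted.
- **The outcome is assigned, not observed.** A reader might say that these women's outcomes are known. SAP 7.1 calls them missing and imputes failure. A woman explanted for infection may have had a 50% reduction in leaks until then.
- **The group is limited.** A woman in a failure category with at least 5 diary days is still scored on her diary in PP (SAP 8.2). Third-line therapy runs against Protocol 10.4 and could be judged a major violation. Compliance below 50% is a separate exclusion. OR1 loses only failures after the one-month diary.
- **Large failure counts are not forecasts.** The pilot had one explant and one personal withdrawal among 36.
- **The exclusions are visible.** SAP 12.1 lists women excluded from each population with the reason, and Protocol 13.3 requires the frequency of and reasons for missing data.

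What these arguments do not remove is the direction of the bias. The SAP judges this missingness informative in one section and sets that judgement aside in the next two. A listing also leaves the reader to rebuild the rate.

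**Conclusion.** The point holds as a bias of known direction and uncertain size in supportive analyses. Women with missing endpoints for reasons that SAP 7.1 itself treats as not missing at random leave the PP denominators and, if SAP 7.3 governs, the OR1 secondary denominators. The primary ITT test is untouched.

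At the only failure-type rate in the documents the effect is small: 1.6 points on a 60% rate, and two fewer responders needed. With 10 failures it is 4.3 points and five fewer. The 70.3% reading is a ceiling that requires every planned dropout to be a listed failure with no major violation.

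These figures assume 150 women, no other PP exclusions and the protocol's exact bound; the SAP's logistic-regression interval was not recomputed. For the OR1 secondary endpoints, SAP 7.3 is the more specific text, but SAP 8.3 and 12.6.2 point the other way, so the handling is unsettled. For the OR1 primary endpoint, the reference back to 7.1 leaves open whether the failure rule applies, and no claim is made there.

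**What to change.** - In SAP 6.1.1, 7.2 and 7.3 and Protocol 13.2.2, state that a woman who meets a SAP 7.1 failure criterion before the time point, has a missing endpoint and has no major violation is kept in PP and OR1 and scored as a non-responder on the dichotomous endpoints. Limit the observed-values rule to data missing for other reasons. The membership wording in 6.1.1 must change together with 7.2, or the rule will have no effect.
- At minimum, keep the observed-case analyses and print beside each PP and OR1 rate the failures-included rate and the number of failures dropped.
- Reconcile SAP 7.2 and 7.3 with SAP 8.3 and 12.6.2, so that the handling of missing secondary endpoints in PP and OR1 has one reading.

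The cost is SAP and protocol wording and a small programming change, using data already collected. The supportive rates will be slightly lower.
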